11.5 Definitions of analysis variables

Formal definitions of variables used in analyses can be found in the Statistical Considerations section of the protocol.

12.0 END OF TREATMENT/INTERVENTION

12.1 Duration of Treatment

12.1.1 CR, PR, or SD: Patients who are in CR, PR or SD will continue on therapy until disease progression/recurrence (or withdrawal of consent). After treatment is discontinued, patients will be followed per the study calendar in [section 5.0](#).

12.1.2 Disease Progression: Patients will be evaluated per [Section 11.0](#). Document details, including tumor measurements, on data forms.

After disease progression, patients should be followed for survival only per the study calendar ([Section 5.0](#)).

12.1.3 Discontinuation of study agent: If the patient discontinues efatutazone, patients should be followed for survival per the study calendar ([Section 5.0](#)).

12.2 Managing ineligible patients and registered patients who never receive protocol intervention

Definition of ineligible patients: A study participant who is registered to the trial but does not meet all of the eligibility criteria is deemed to be ineligible. Patients who are deemed ineligible may continue protocol treatment, provided the treating physician, study chair, and executive officer agree there are no safety concerns if the patient continues protocol treatment. All scans, tests, and data submission are to continue as if the patient were eligible. Notification of the local IRB may be necessary per local IRB policies.

Study participants who are registered to the trial but never receive study intervention (for a reason other than because they were deemed ineligible) must still complete follow-up requirements as specified below.

Baseline, on-study and off-treatment notice data submission required.

12.3 Extraordinary Medical Circumstances

If, at any time the constraints of this protocol are detrimental to the patient's health and/or the patient no longer wishes to continue protocol therapy, protocol therapy shall be discontinued. In this event:

- Document the reason(s) for discontinuation of therapy on data forms.
- Follow the patient for protocol endpoints as required by the Study Calendar.

13.0 STATISTICAL CONSIDERATIONS

13.1 Study Overview

This single arm Phase II trial will assess the confirmed response rate of efatutazone in patients with advanced, unresectable, or metastatic myxoid liposarcoma who have received at least one prior systemic therapy. Prior studies have shown that the confirmed response rate is generally around 5%. It is hoped that efatutazone can increase the confirmed response rate to at least 20%. In addition to the confirmed response rate, this trial will also estimate the progression-free survival (PFS), overall survival (OS), and adverse event rates for efatutazone.

13.2 Primary Endpoint and Study Design

The primary endpoint for this study will assess the confirmed response rate (by RECIST 1.1) of efatutazone in patients with advanced, unresectable, or metastatic myxoid liposarcoma who have received at least one prior systemic therapy. Any confirmed response that occurs during the first 8 cycles of treatment will count as a success (24 weeks). Per RECIST 1.1, responses need to be confirmed (2 consecutive responses at least 4 weeks apart) to count as a response (see Section 11). All eligible patients who are registered and start treatment will be evaluable for response. A Simon's optimal two-stage design will be utilized (see below). This design has 80% power to detect an improvement in the confirmed response rate from 5% to 20%, with a significance level of 0.10. See design details below:

Interim Analysis: Enroll 9 eligible patients (need 6 additional patients after design change to single arm trial). If at least 1 confirmed response is observed in the first 9 eligible patients, we will continue the study to a full accrual of 24 eligible patients. Otherwise, the study will be permanently closed due to lack of efficacy. The study will remain open during the interim analysis phase due to slow projected accrual rate and minimal expected toxicity.

Final Analysis: If the trial is a success during the interim analysis, we will enroll another 15 eligible patients (24 eligible total). If at least 3 confirmed responses are observed in the first 24 eligible patients (13%), the treatment will be considered worthy of further investigation. Otherwise, the study will be permanently closed due to lack of efficacy.

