 - 2 For women of childbearing potential (see [Section 3.3](#)). Must be done \leq 7 days prior to registration and \leq 7 days prior to re-registration at crossover.
 - 3 See [Sections 4.5](#) and [6.1](#).
 - 4 Baseline scans can include either: 1) a CT, spiral CT, or MRI, or 2) an FDG-PET scan and diagnostic CT performed with both IV and oral contrast, and the CT acquired with 5 mm or less slice thickness. If a bone scan is used for baseline scan, please note in ECRF, but bone scans are not mandatory. Documentation (radiologic and pathology report and clinic note) of the diagnosis scan must be submitted.
 - 5 Fasting triglycerides and total cholesterol will be done on Day 1 of Cycles 3 and 6 (+/- 7 days).
- A Every 6 weeks (approximately every 2 cycles) through 24 weeks, and then every 12 weeks (approximately every 4 cycles) after week 24 until evidence of progression or relapse. Scans may be done up to 7 days prior to beginning a cycle. Confirmatory scans should also be obtained at least 4 weeks following documentation of objective response (see [Section 11.0](#)).
If the baseline scans were a CT or MRI and bone scan, follow-up bone scans are required only for patients with bone metastases as the only site of evaluable disease, and are optional for other patients. **Response assessment should include assessment of all sites of disease and use the same imaging method as was used at baseline.** Documentation (radiologic and clinic note) must be provided at progression of disease.

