7.0 TREATMENT PLAN/INTERVENTION

Protocol treatment is to begin ≤ 7 days from registration.

Patients are permitted to have a new cycle of treatment delayed up to 7 days for major life events (e.g., serious illness in a family member, major holiday, vacation that cannot be rescheduled) without this being considered a protocol violation. Documentation to justify this delay should be provided.

Patients will receive efatutazone, 0.5mg orally twice daily. Each cycle is 21 days (3 weeks).

If at reimaging there is no evidence of disease progression, and the patient is tolerating therapy, then the patient will continue to remain on treatment until progression.

A091202 dose table:

Agent	Dose	Route	Day	ReRx
Efatutazone	0.5 mg	PO	BID	Every 21 days*

*Taken continuously with no break between cycles

Efatutazone tablets are to be self-administered PO BID, with or without food. The intended dosing schedule for efatutazone dosing is every 12 hours. However, dosing may occur within ± 2 hours of the scheduled administration time.

Treatment is to continue until disease progression or unacceptable adverse event. After disease progression or unacceptable adverse event, patients will be followed for a maximum of 5 years, as in [Section 5.0](#).

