11.0 MEASUREMENT OF EFFECT

Response and progression will be evaluated in this study using the new international criteria proposed by the revised Response Evaluation Criteria in Solid Tumors (RECIST) guidelines (version 1.1). Changes in the largest diameter (unidimensional measurement) of the tumor lesions and the short axis measurements in the case of lymph nodes are used in the RECIST guideline.

11.1 Schedule of Evaluations:

For the purposes of this study, patients should be reevaluated every 6 weeks (approximately every 2 cycles) during treatment. Of note, scans should be performed according to the Study Calendar in [Section 5.0](#). In addition to a baseline scan, confirmatory scans should also be obtained ≥ 4 weeks following initial documentation of objective response

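### Does it matter that Section 13.2 does not say which scan dates a confirmed response?

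*Combined protocol and SAP*

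**What the plan says.** Section 13.2 sets the window and the confirmation rule in consecutive sentences: "Any confirmed response that occurs during the first 8 cycles of treatment will count as a success (24 weeks"), and then "responses need to be confirmed (2 consecutive responses at least 4 weeks apart) to count as a response". The same paragraph states the sizing: 80% power for an improvement in the confirmed response rate from 5% to 20% at a significance level of 0.10. The study continues past 9 eligible patients with at least 1 confirmed response, and is positive with at least 3 among 24.

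Note A of the Study Calendar (Section 5.0) schedules scans "Every 6 weeks (approximately every 2 cycles) through 24 weeks, and then every 12 weeks (approximately every 4 cycles) after week 24", and adds that "Scans may be done up to 7 days prior to beginning a cycle". Section 11.1 says that "confirmatory scans should also be obtained ≥ 4 weeks following initial documentation of objective response"; the calendar note says the same. Neither gives a latest date for confirmation.

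Section 11.5 refers to the Statistical Considerations for formal definitions of analysis variables, and Section 13 has none for the date of response. The explicit dating rule in Section 11.3.2 concerns progression by FDG-PET.

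**The concern.** A confirmed response needs two scans, and the plan does not say which of them must fall in the first 8 cycles. If both must, a patient whose response is first seen at week 24 and later confirmed counts as a failure. If the first scan dates the response, the same patient is a success.

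The decision rules are small-number rules, so one patient can settle them. On the stricter reading, a trial whose only stage-1 responder was first seen at week 24 would close permanently for lack of efficacy despite a confirmed RECIST response. The trial is now open label and single arm, so a choice made after the responses are known could be driven by the data.

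Two further points add to the doubt. The window is given both as 8 cycles and as 24 weeks, and Section 7.0 says that "Patients are permitted to have a new cycle of treatment delayed up to 7 days for major life events", so the two can diverge. Section 13.1 also states the 5% and 20% rates without a window.

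**Working it through.** **1. Which responses are affected.** The window is 8 × 21 = 168 days = 24 weeks, so the two units agree when cycles run on time. Scans fall at weeks 6, 12, 18 and 24, then at week 36. With scans on schedule, a response first seen at week 6, 12 or 18 can be confirmed from week 10, 16 or 22, and the next routine scan is at week 12, 18 or 24. Both readings agree on these patients. The week-24 scan may be done in weeks 23 to 24, so its earliest confirmation is 23 + 4 = 27 to 24 + 4 = 28 weeks. Only the last of the four scans is ambiguous.

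**2. The plan's own figures.** Let p be the true rate of the counted endpoint, X1 the responses in the first 9 patients, X2 those in the next 15, and X = X1 + X2. The treatment passes if X1 ≥ 1 and X ≥ 3, so

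P(pass) = P(X ≥ 3 of 24) − P(X1 = 0 of 9) × P(X2 ≥ 3 of 15).

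- p = 0.05: 0.1159 − 0.6302 × 0.0362 = 0.093 (type I error).
- p = 0.20: 0.8855 − 0.1342 × 0.6020 = 0.805 (power).

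A grid search over two-stage designs for 5% against 20% (type I error at most 0.10, power at least 0.80) also returns 0/9 and 2/24 as the optimal design.

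**3. If the rates describe the endpoint as scored.** P(pass) depends only on p. If 5% and 20% are the rates of the endpoint under whichever dating rule is used, type I error is 0.093 and power 0.805 under both rules.

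**4. If they do not match.** Let f be the share of confirmed responders first seen at week 24. The documents give no value, so 5% and 10% are illustrations.

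| Assumption | Rates entered | f = 5% | f = 10% |
|---|---|---|---|
| Rates include week-24 responders, scoring excludes them | 0.20(1 − f) = 0.19, 0.18 | power 0.777 | power 0.745 |
| Same | 0.05(1 − f) = 0.0475, 0.045 | type I error 0.083 | type I error 0.073 |
| Rates exclude them, scoring includes them | 0.05/(1 − f) = 0.0526, 0.0556 | type I error 0.105 | type I error 0.118 |
| Same | 0.20/(1 − f) = 0.2105, 0.2222 | power 0.831 | power 0.856 |

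The two assumptions exclude each other. In each, one error rate worsens and the other improves.

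**5. How often the readings would disagree.** Take p as the rate when the first scan dates the response.

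- Stage 1: the readings differ when no response is confirmed within the window but at least one week-24 response is later confirmed. The probability is (1 − p(1 − f))^9 − (1 − p)^9. At p = 0.20 this is 0.1501 − 0.1342 = 0.016 (f = 5%) or 0.1676 − 0.1342 = 0.033 (f = 10%). At p = 0.05 it is 0.015 or 0.031.
- Overall verdict: every success on the strict reading is also a success on the lenient one, so the disagreement is the difference in P(pass). At p = 0.20: 0.8047 − 0.7766 = 0.028, or 0.8047 − 0.7451 = 0.060. At p = 0.05: 0.0931 − 0.0828 = 0.010, or 0.0931 − 0.0731 = 0.020.

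**The case for a change.** The strongest case for a change is that the primary endpoint of a 24-patient trial should leave nothing to judgement. The calendar makes the week-24 case foreseeable, the design has little slack (power falls below 0.80 if more than 0.9% of responders are lost), and a sentence in Section 13.2 would cost almost nothing. Trials near a boundary are also common: the chance of exactly 1 response in 9 is about 30% at either rate, and that of exactly 3 in 24 after passing stage 1 is 11.6% at 20% and 6.7% at 5%.

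The gap in the text stands, and so does the preference for settling the date before the counts are seen. The rest carries less weight. The boundary probabilities say how often one responder is decisive, not how often that responder was first seen at week 24. The 0.9% figure reflects a power of 0.805 against a target of 0.80, and it applies only under one mismatch assumption.

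The two readings are not evenly balanced either. What must occur in the window is a confirmed response, and the next sentence says a response must be confirmed in order to count. Confirmation inside the window is arguably the more literal reading, and analysts can start from it. Dating by the first scan is also defensible, but it takes type I error above 0.10 if the 5% was a windowed rate and f exceeds 3.1%, and it would need a latest confirmation date. Reasonable statisticians could choose either.

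The point about cycles and weeks is minor. The units coincide unless a cycle is delayed, the quoted allowance is a documented exception, and the scan schedule is itself set in weeks.

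**Conclusion.** No change to the plan follows. Section 13.2 leaves out a dating convention for responses first seen at the week-24 scan, which analysts can supply when they score the endpoint. The design is correctly sized as stated, with type I error 0.093 and power 0.805 under either convention. This rests on reading the 5% and 20% as rates of the endpoint defined in the same paragraph, which is the natural reading.

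Shifts in power to 0.777 or 0.745, or in type I error to 0.105 or 0.118, need both a mismatch between rates and endpoint and an assumed share f of 5% or 10%. The documents establish neither. On those same shares the readings would part at stage 1 in about 1.5% to 3% of trials, and on the overall verdict in about 1% to 6%. Accrual stays open during the interim analysis, so if a team chose to wait 4 to 12 weeks for a pending confirmation, about 1 to 3 further patients would enrol at the expected 1 per month. Either convention gives a sound answer to the question the trial asks.

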13.3 Secondary Endpoints

The following endpoints will be assessed: progression-free survival, overall survival, and adverse events. All patients who meet the eligibility criteria, and sign the consent form will be considered evaluable for these endpoints.

Progression-Free Survival: Progression-free survival (PFS) is defined as the time from study entry to the first of either disease progression or death from any cause, where disease progression will be determined based on RECIST 1.1 criteria. PFS will be estimated using the Kaplan-Meier method.

Overall Survival: Overall survival (OS) is defined as the time from study entry to death from any cause. OS will be estimated using the Kaplan-Meier method.

Adverse events: The maximum grade for each type of adverse event will be summarized using CTCAE version 4.0. The frequency and percentage of grade 3+ adverse events will be estimated.

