2.2 Secondary objective

2.2.1 To assess the progression free survival (PFS), overall survival (OS), and adverse event rates for efatutazone treated patients with advanced myxoid liposarcoma whose disease has progressed on at least one prior therapy.

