8.3 Unblinding Procedures (prior to update #02)

As of 10/01/16, the study was redesigned from a double-blind placebo controlled study to an open label single arm study of efatutazone, due to slow accrual to the trial. Therefore, on 10/01/16 the study was unblinded and all participants were placed on open label efatutazone.

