13.5 Total Sample Size, Accrual Duration, and Anticipated Time to Study Completion

A maximum of 24 evaluable patients (21 new efatutazone treated patients + 3 already randomized previously) will be accrued onto this randomized phase II study unless the study is closed early for excessive toxicity or lack of efficacy. We anticipate accruing an additional 20% of patients to account for ineligibility, cancellation, major treatment violation, or other reasons. Therefore, maximum accrual is about 30 patients (up to 28 treated with efatutazone (25 new, 3 already enrolled) + 2 placebo treated patients (already enrolled from prior randomized study)). With an expected accrual rate of 1 patient per month, we anticipate that it will take about 3 years to reach full accrual. We anticipate that the study will take approximately 4 years to complete. This allows a 6-month follow-up for the final patient enrolled, along with data entry and analysis.

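### Section 13.3 gives adverse events the same eligible-and-consented set as PFS and OS; read literally, it would leave dosed but ineligible patients out of the AE summary

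*Combined protocol and SAP*

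**What the plan says.** Section 13.3 lists three secondary endpoints (PFS, OS and adverse events) and then gives one population for all of them: "All patients who meet the eligibility criteria, and sign the consent form will be considered evaluable for these endpoints". The adverse event paragraph that follows describes the summary (highest grade per event type, and the proportion with grade 3 or worse) and names no other set.

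Four other places bear on this:

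- **Section 2.2.1** states the objective as "adverse event rates for efatutazone treated patients with advanced myxoid liposarcoma" that has progressed on prior therapy.
- **Section 12.2** defines an ineligible patient as one who was registered but fails a criterion. It then says "Patients who are deemed ineligible may continue protocol treatment", subject to agreement that there is no safety concern, and adds "All scans, tests, and data submission are to continue as if the patient were eligible".
- **Section 13.2** sets a different condition for the primary endpoint: "All eligible patients who are registered and start treatment will be evaluable for response".
- **Section 13.6** bases the AE stopping rule on treated patients for the first nine, and on all patients after that. It does not restrict the count to eligible patients.

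**The concern.** The usual population for a toxicity summary is everyone exposed to the drug, because a failed entry criterion does not undo the exposure. Section 13.3 instead conditions the AE summary on eligibility. The protocol foresees that some ineligible patients will be dosed and collects their data in full. Following section 13.3 as written would then drop those data from the one table in which the trial reports its AE rates.

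The stake is the accuracy and completeness of that table. In a trial of about two dozen patients, one omitted patient changes a percentage visibly. If that patient had the only occurrence of an uncommon event, the table would show none. The stopping rule and the AE summary could also rest on different groups of patients.

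A lesser wording point runs the other way. Section 13.3 does not require that treatment was started, so an eligible patient who never took a dose could enter the AE denominator. The section is also silent on the 2 patients first assigned to placebo.

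**Working it through.** **1. The plan's own counts (section 13.5).** Evaluable: 21 new + 3 already randomized = 24. The 20% allowance on the new patients gives 21 × 1.2 = 25.2, stated as 25. Efatutazone-treated: 25 + 3 = 28. With the 2 placebo patients: 28 + 2 = 30. The plan's figures reproduce.

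**2. How many patients could be affected.** Section 13.5 allows for "up to 28 treated with efatutazone (25 new, 3 already enrolled"), against 24 evaluable. The margin is 28 − 24 = 4 patients, or 4/28 = 14.3% of those treated. It exists "to account for ineligibility, cancellation, major treatment violation, or other reasons", so ineligibility is only one of its uses. The number dosed but ineligible therefore lies between 0 and 4 at full accrual and is probably below 4.

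This ceiling leaves out the 2 patients first assigned to placebo. Section 8.3 reports that "the study was unblinded and all participants were placed on open label efatutazone", while section 13.5 counts these 2 apart from the 28. If both took efatutazone, the all-dosed total could reach 30.

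**3. Largest effect of one omitted patient.** Suppose the table reports x events in 24 patients.

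- Omitted patient had the event: (x + 1)/25 − x/24 = (24 − x)/600. The largest value is at x = 0: 24/600 = 4.0 points (0/24 reported, 1/25 among all dosed).
- Omitted patient did not have the event: x/25 − x/24 = −x/600. The largest fall is at x = 24, also 4.0 points.
- At an assumed x = 6: up 18/600 = 3.0 points (25.0% to 28.0%), or down 6/600 = 1.0 point (25.0% to 24.0%).

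**4. Illustration over the whole range.** Assume the table reports 6/24 = 25.0% with a grade 3 or worse event (exact 95% interval 9.8% to 46.7%). Let k be the number dosed but ineligible, with between none and all of them affected.

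| k | All-dosed rate, lowest | All-dosed rate, highest |
|---|---|---|
| 0 | 6/24 = 25.0% | 6/24 = 25.0% |
| 1 | 6/25 = 24.0% | 7/25 = 28.0% |
| 2 | 6/26 = 23.1% | 8/26 = 30.8% |
| 3 | 6/27 = 22.2% | 9/27 = 33.3% |
| 4 | 6/28 = 21.4% | 10/28 = 35.7% |

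The 6 events and each k are assumptions. Every value lies inside the interval for 6/24, and the direction of the shift is not known in advance.

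**5. Chance of missing an uncommon event.** If the true rate of some event is 5% (an assumption), the chance that at least one of k omitted patients has it is 1 − 0.95^k: 5.0% for k = 1 and 18.5% for k = 4.

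**6. The never-dosed point.** One eligible, undosed, event-free patient added to the denominator turns 6/24 = 25.0% into 6/25 = 24.0%.

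**7. What does not move.** The response design uses its own set in section 13.2. Its exact operating characteristics (at least 1 of 9, then at least 3 of 24) are a type I error of 0.0931 at 5% and power of 0.8047 at 20%, consistent with the stated 0.10 and 80%. Nothing here alters them.

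**The case against.** The best defense is that section 13.3 says who is evaluable without saying that nobody else may be tabulated. No section tells the analyst to delete ineligible patients from AE tables. The stopping rule already looks at treated patients, and section 12.2 keeps the data flowing. On this view the AE set is merely under-specified. That is a fair reason to word the point conditionally, but it does not remove it. Section 13.6 governs only the stopping rule, section 12.2 governs data submission and not analysis, and the one sentence that does define the AE population conditions it on eligibility.

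Second, objective 2.2.1 itself carries two entry conditions: myxoid liposarcoma, and progression on prior therapy. A dosed patient who was ineligible on either ground is outside the objective too, so there section 13.3 and the objective agree. This stands in part. The mismatch remains for patients who fail on other grounds, such as laboratory values or effusion history.

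Third, such patients may be rare. Pathology is confirmed centrally before registration, and section 3.0 rules out eligibility waivers. This stands, and it is why zero is within the range.

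A reader might also infer that the omission would hide the patients at highest risk, since several entry criteria concern effusions, heart failure and insulin use, and fluid retention is a known effect of the drug. The documents do not show that any such patient was or will be enrolled, so no bias in a particular direction can be claimed.

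**Conclusion.** The point holds as a defect in the stated rule for one descriptive table. Followed as written, section 13.3 would leave out toxicity data that the trial has collected on patients who took the drug. This sits poorly with objective 2.2.1 and with the treated-patient basis of section 13.6.

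The size is small and uncertain: 0 to 4 patients at full accrual, not counting the 2 first assigned to placebo, and at most 4.0 percentage points for one patient omitted from a set of 24. This assumes that 24 eligible patients are reached; closure at the interim analysis would leave a smaller set, in which one patient weighs more.

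Three stronger readings are not supported:

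- **That safety oversight is compromised.** Data collection, expedited reporting and the stopping rule do not depend on section 13.3.
- **That the plan intends to dilute AE rates with undosed patients.** Objective 2.2.1 refers to treated patients, so the missing start-of-treatment condition looks unintended.
- **That the handling of the placebo-first patients is contradictory.** Section 13.3 is silent on them, which is a gap to clarify.

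The PFS and OS population is not in question. The change should be made because it costs almost nothing and because choosing the AE set after the data are seen would be a departure from the written plan.

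**What to change.** In section 13.3, keep the eligible-and-consented set for PFS and OS and add one sentence: *Adverse events will be summarized in all patients who received at least one dose of efatutazone, regardless of eligibility.* This also takes eligible but never-dosed patients out of the AE denominator.

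As a secondary clarification, state that events during the placebo period of the 2 placebo-first patients are not counted as efatutazone events, and that any events after their first efatutazone dose are identified separately.

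The cost is one sentence plus the clarification. No new data, patients or change to AE collection is needed, because section 12.2 already requires full data submission for ineligible patients.

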5.0 STUDY CALENDAR

Laboratory and clinical parameters during treatment are to be followed using individual institutional guidelines and the best clinical judgment of the responsible physician. It is expected that patients on this study will be cared for by physicians experienced in the treatment and supportive care of patients on this trial.

Pre-Study Testing Intervals

- To be completed \leq 14 DAYS before registration: All laboratory studies, history and physical.
- To be completed \leq 28 DAYS before registration: Any imaging modality which is utilized for tumor measurement per protocol.
- To be completed \leq 42 DAYS before registration: Any baseline exams used for screening, or any imaging of any type which is not utilized for tumor measurement.

	Prior to Registration *	Days 1 (+/- 4 days) of each cycle through Cycle 4; then Day 1 (+/- 7 days) of every odd numbered cycle for Cycle 5 and beyond	Weeks 2 and 3 (+/- 2 days) of Cycle 1	Post treatment follow up***	At PD, withdrawal, or removal****
Tests & Observations					
History and physical, weight, PS	X	X	X	X	X
Height	X				
Pulse, Blood Pressure	X	X	X		
Adverse Event Assessment		X	X		X
Registration Fatigue/Uniscale Assessment	X(1)				
Laboratory Studies					
Complete Blood Count, Differential, Platelets	X	X			
Creatinine,	X	X			
Albumin, glucose	X	X			
AST, ALT, Alk. Phos., Bili	X	X			
Fasting Triglycerides, total cholesterol		X(5)			
Serum or Urine HCG	X(2)				
Staging					
Central pathology review for eligibility	X(3)				
Tumor Measurement	X	A		X	
CT/MRI chest/abdomen/pelvis	X(4)	A		A	
A091202-ST1 Correlative studies: For patients who consent to participate					
Archival block OR slides	X				

- * Labs completed prior to registration may be used for day 1 of cycle 1 tests if obtained \leq 14 days prior to treatment.
- *** For patients who are removed from protocol therapy for reasons other than progression: Physical examination and staging scans are required every 12 weeks (+/- 7 days) (after the end of treatment) until disease progression. On completion of study treatment, all patients are followed for survival only every 6 months (+/- 30 days) until death or a maximum follow-up of 5 years. See also [Section 12.0](#).
- **** Visit and AE assessment should be completed 4 weeks (+/- 7 days) after completion of protocol therapy
 - 1 To be completed after pre-registration and prior to registration, see [Appendix I](#).

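### Section 13.3 does not require patients to start efatutazone to count for PFS, OS and adverse events, which conflicts with objective 2.2.1 and the response set in 13.2

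*Combined protocol and SAP*

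**What the plan says.** Four parts of the combined protocol and SAP bear on this.

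- **Objective 2.2.1** asks for PFS, OS and "adverse event rates for efatutazone treated patients with advanced myxoid liposarcoma" after at least one prior therapy. The population is the treated one.
- **Section 13.2**, for the primary endpoint: "All eligible patients who are registered and start treatment will be evaluable for response".
- **Section 13.3**, for PFS, OS and adverse events together: "All patients who meet the eligibility criteria, and sign the consent form will be considered evaluable for these endpoints". Neither registration nor a first dose is mentioned. PFS is "the time from study entry to the first of either disease progression or death from any cause", and OS has the same origin. No censoring rule is given for a patient who never starts.
- **Section 12.2** says that registrants who never receive the intervention "must still complete follow-up requirements as specified below". What follows is a single line: "Baseline, on-study and off-treatment notice data submission required". For ineligible patients the same section says: "All scans, tests, and data submission are to continue as if the patient were eligible".

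The calendar in section 5.0 ties its later contacts to treatment: "On completion of study treatment, all patients are followed for survival only every 6 months". Its 12-weekly staging scans are for patients taken off protocol therapy for a reason other than progression. Section 13.5 names cancellation among the reasons for accruing beyond 24 evaluable patients.

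**The concern.** The condition that a patient must start treatment is present in 13.2 and gone in 13.3. An eligible patient who registers and then cancels is outside the response analysis but inside PFS, OS and adverse events. Followed literally, 13.3 does not estimate what objective 2.2.1 states.

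Two things are at stake. An adverse event rate for efatutazone would be computed over some patients who never took it. PFS and OS would include patients for whom the plan does not clearly require any outcome data. In a trial of about 24 patients, leaving this open also means the denominator could be chosen after the data are seen.

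**Working it through.** **1. The plan's own design figure.** Section 13.2 states 80% power and a significance level of 0.10 for 5% against 20%, with 9 then 24 patients, continuing on at least 1 response and succeeding on at least 3. The probability of success is the sum over x = 1 to 9 of C(9,x) p^x (1−p)^(9−x) × P(Y ≥ 3−x), with Y binomial(15, p). This gives 0.0931 at p = 0.05 and 0.8047 at p = 0.20, so the stated design is reproduced. Section 13.2 already uses patients who start treatment, so nothing below changes it.

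**2. How many patients could be involved.** Section 13.5 gives 24 evaluable and up to 28 efatutazone patients, so the allowance is 28 − 24 = 4. With k never-dosed patients added to 24, their share is k/(24 + k):

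- k = 1: 1/25 = 4.0%
- k = 2: 2/26 = 7.7%
- k = 4: 4/28 = 14.3%

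Four is an upper bound by assumption. The allowance also covers ineligibility, treatment violations and other reasons, and 13.5 describes the 28 as treated.

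**3. Adverse events.** With x affected patients among 24 treated, the reported rate is x/(24 + k). Taking x = 6 as an illustration (25%):

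- k = 1: 6/25 = 24.0%
- k = 2: 6/26 = 23.1%
- k = 4: 6/28 = 21.4%

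The dilution factor 24/(24 + k) applies whatever x is. Censoring offers no protection here.

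**4. PFS and OS, three cases.** The PFS curves are taken as exponential, and the medians only set the scale.

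- *Censored at entry.* The patients leave the risk set before the first event. The Kaplan-Meier curve is unchanged and only the stated N is inflated.
- *Fully followed.* Solve (1−w) × 2^(−t/5.5) + w × 2^(−t/m) = 0.5 with w = k/(24 + k). The 5.5 months is the rosiglitazone trial median in section 1.3, and m is an assumed never-treated median of 2.0 to 3.3 months. The pooled median is 5.28–5.38 months for k = 1, 5.08–5.28 for k = 2 and 4.73–5.10 for k = 4.
- *Extreme.* Four are never dosed, two fail before dosing and two are censored at entry. Then S = 24/26 = 0.923. With a treated median of 3.3 months (the trabectedin expanded access figure in section 1.1), 0.923 × 2^(−t/3.3) = 0.5 gives t = 2.92 months, about 12% lower.

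**5. How likely the extreme case is.** Section 7.0 has treatment begin within 7 days of registration, and 7/30.4 = 0.23 months. At a 3.3-month median the 7-day event risk is 1 − 2^(−0.23/3.3) = 4.7%. The chance of two or more events in four patients is 1 − 0.953^4 − 4 × 0.047 × 0.953^3, about 1%. Never-dosed patients may be sicker than average, but the documents give no figure for that. For scale, with 24 events the standard error of the log median is about 1/√24 = 0.20. The shift is ln(3.3/2.92) = 0.12, or 0.6 standard errors, and the 95% interval around 3.3 months would run from about 2.2 to 4.9.

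**6. What restricting the set could do in the other direction.** Time still runs from study entry, so a patient in the restricted set must be event-free until the first dose. If every patient started on day 7, an exponential median of 3.3 months would become 3.3 + 0.23 = 3.53 months. Earlier starts make the shift smaller.

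**The case against.** **An all-eligible set is a legitimate choice for PFS and OS.** It matches the study-entry origin, and limiting the set to patients who start removes early failures by conditioning on a later event. That stands as a cost of the change (step 6). It does not rescue the current text. The trial is now single-arm, so there is no randomised comparison to protect. The plan's own objective names treated patients, and an all-eligible set would need outcome follow-up that 12.2 does not specify. The argument has no force for adverse events.

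**Follow-up may have been intended.** The lead-in in 12.2 speaks of follow-up requirements, and 12.3 asks sites to follow patients who no longer wish to continue therapy for protocol endpoints per the calendar. But 12.3 is written for therapy being discontinued, and the calendar for treatment completed or stopped. Follow-up of a never-dosed patient is at best unclear, which is less than saying that none would be collected.

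**One-sided event capture.** A reader might infer that the off-treatment notice would record deaths and progressions before dosing while patients who decline leave no data. The documents do not describe the content of that notice or of the on-study forms, so this is not established.

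**A median PFS about 12% too low.** A reader might also take 2.9 against 3.3 months as the expected bias. It needs the whole allowance to be eligible never-dosed patients and half of them to fail inside a 7-day window. It is an extreme illustration.

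**Conclusion.** The inconsistency stands. Section 13.3 defines a wider population than objective 2.2.1 and section 13.2, and section 12.2 specifies no scans or survival contacts for the extra patients. Never-dosed patients would dilute adverse event rates directly, by a factor of 24/28 = 0.857 at most under the 13.5 allowance and by less with one or two such patients. The effect on PFS and OS runs from none to a modest lowering, and is probably small given the 7-day start window. All sizes rest on an assumed number of eligible never-dosed registrants, and those for PFS also on exponential curves. These endpoints are secondary and descriptive, and the primary decision rule is unaffected. The point concerns never-dosed patients and does not depend on those first randomised to placebo.

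**What to change.** In 13.3, define one analysis set for PFS, OS and adverse events: eligible, registered patients who start efatutazone. This matches 2.2.1 and 13.2. Adverse events must be included in the change, or a new mismatch replaces the old one. List never-treated registrants separately, with the reason and any known outcome.

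The cost is one or two sentences and no new data. The stated N falls by the few never-treated patients. Because time still runs from study entry, leaving out pre-dose failures could raise PFS and OS slightly, and the report should say so.
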